#### General analysis conventions

**Pooling of centers:** Unless specified otherwise, data from all study centers will be pooled for the analysis. No center effect will be assessed.

**Qualitative data** (e.g., ECOG, race, etc.) will be summarized by tables; a missing category will be included as applicable. Percentages will be calculated using the number of participants in the relevant population or subgroup as the denominator.

**Quantitative data** (e.g., age, body weight, height, etc.) will be summarized by appropriate descriptive statistics (i.e. mean, standard deviation, median, 1st and 3rd quartiles, minimum, and maximum).

#### 2.1.1 General definitions

#### Investigational PET imaging agent: [F]CTT1057

**Study treatment:** a single injection intravenously (i.v.) of approximately 370 MBq (range 266 – 407 MBq) [F]CTT1057 whether the PET/CT scan was acquired or not.

#### Date of administration of investigational PET imaging agents

The date of administration of investigational PET imaging agent is defined as the date when a non-zero dose of investigational PET imaging agent is administered and recorded on the study treatment (e)CRF. The date of administration of study treatment will also be referred as start of investigational PET imaging agent.

#### Study day

The study day describes the day of the event or assessment date, relative to the reference start date.

The study day is defined as:

- The date of the event (visit date, onset date of an event, assessment date etc.) reference start date + 1 if event is on or after the reference start date;
- The date of the event (visit date, onset date of an event, assessment date etc.) reference start date if event precedes the reference start date.

Novartis	Confidential	Page 15 of 43
SAP Amendment 2		Study No. CAAA405A12302

The reference date for all assessments (safety, efficacy, pk, etc) is the start of study treatment.

The study day will be displayed in the data listings. If an event starts before the reference start date, the study day displayed on the listing will be negative.

#### Time unit

A year length is defined as 365.25 days. A month length is 30.4375 days (365.25/12). If duration is reported in months, duration in days will be divided by 30.4375. If duration is reported in years, duration in days will be divided by 365.25.

#### Baseline

For safety evaluations, the last available assessment prior to the administration of [F]CTT1057 (on or before the start of the study treatment date/time) is defined as "baseline" assessment. If participants have no value as defined above, the baseline result will be set to matching missing.

Efficacy evaluations will not include any comparisons between baseline and post-baseline values, and therefore a baseline definition for efficacy evaluations does not apply.

#### On-treatment assessment/event and observation periods

For adverse event reporting, the overall observation period will be divided into three mutually exclusive segments:

- 1. **Pre-treatment period:** from day of participant's informed consent to the day and time before dosing of study medication.
- 2. **On-treatment period:** from day of dosing of study medication to 14 days after dosing of study medication.
- 3. Post-treatment period: starting 15 days after dosing of study medication.

Safety summaries (tables, figures) include only data from the on-treatment period with the exception of baseline data which will also be summarized where appropriate (e.g. change from baseline summaries). In addition, a separate summary for death including on-treatment and post-treatment deaths will be provided. In particular, summary tables for adverse events (AEs) will summarize only on-treatment events, with a start date during the on-treatment period (*treatment-emergent* AEs).

However, all safety data (including those from the post-treatment period) will be listed and those collected during the pre-treatment and post-treatment period will be flagged.

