
 
Characterize the safety and tolerability of [F]CTT1057
 
	
 
Incidence of AEs. Treatment emergent adverse event (TEAE) rate within 14 days of administration
 

 
[F]CTT1057 scan inter-reader variability
 
	
 
Inter-reader agreement of [F]CTT1057 images
 

Objective(s)	Endpoint(s)

 
[F]CTT1057 scan intra-reader variability
 
	
 
Intra-reader agreement of [F]CTT1057 images
 

 
To further assess [F]CTT1057 pharmacokinetics in humans in subset of approximately 10 patients
 
	
 
Summary statistics of [F]CTT1057 pharmacokinetic parameters (i.e. Cmax, Tmax, AUClast, AUCinf, T1/2, Vz and CL from blood radioactivity data; quantification of urinary excretion of [F]CTT1057 from urine data)
 

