#### **Additional Follow-up**

Surgery (RP/ePLND) will be scheduled for all participants as planned per SoC on a date that must not be sooner than 48 hours after the completion of the [ $^{18}\text{F}$ ]CTT1057 PET/CT scan, and no later than 6 weeks after completion of the [ $^{18}\text{F}$ ]CTT1057 PET/CT scan. Final histopathology results have to be obtained within 2 weeks after surgery.

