## 12.5.2 Safety endpoints

For all safety analyses, the SAF will be used.

Safety summaries (tables, figures) include only data from the on-treatment period with the exception of baseline data which will also be summarized where appropriate (e.g. change from baseline summaries). In addition, a separate summary for death including on treatment and post treatment deaths will be provided. In particular, summary tables for AEs will summarize only on-treatment events, with a start date during the on-treatment period (treatment-emergent AEs).

The overall observation period will be divided into three mutually exclusive segments:

1. Pre-treatment period: from day of participant's informed consent to the day and time before dosing of study medication.
2. On-treatment period: from day of dosing of study medication to 14 days after dosing of study medication.
3. Post-treatment period: starting 15 days after dosing of study medication.

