## 1.1 Study design

This is a multi-center, single-arm, open-label prospective study to evaluate the diagnostic performance of [F]CTT1057 as a PET imaging agent for detection and localization of PSMA positive tumors, using histopathology as SoT. Tissue specimens from both the primary tumor and pelvic lymph nodes (PLN) dissected during surgery from participants with newly-diagnosed high-risk prostate cancer (PCa) will be used for the histopathology assessments.

Approximately 195 participants will be enrolled to ensure that at least 156 participants are evaluable for co-primary endpoints. Surgery (radical prostatectomy/ePLND) will be performed up to 6 weeks after [F]CTT1057 PET/CT but not sooner than 48 hours after the completion of the [F]CTT1057 PET/CT scan (in order to limit the potential confounding factors related to the effects of surgery for the assessment of [F]CTT1057 PET/CT safety) for pathology assessment of the tissue specimens.

The co-primary endpoints of patient-level sensitivity and region-level specificity will be assessed by comparing the central reading results of the  $[^{18}F]CTT1057$  PET/CT scan (see Section 4.1 and Section 8.3.1 for central read details and Section 6.4 for blinding details of the protocol) to the histopathology results in the dissected tissue specimens, i.e. both the primary tumor and the dissected PLNs (Maurer et al 2016, Woythal et al 2018, Kuten et al 2020).

Pathology will be assessed by the local pathologists as per Standard of Care (SoC). Pathologists will be blinded to the PET data. For anatomical localization, a sextant anatomic template for the prostate and a left/right template for the PLNs will be used (see appendix Section 16.3 of the protocol). Pathology results should be available within 2 weeks after surgery.

See Figure 1-1 for study design

schema. There will be no interim analysis for this study.

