#### 2.4 Treatments (study treatment, rescue medication, concomitant therapies, compliance)

#### 2.4.1 Study treatment / compliance

The following exposure information of [F]CTT1057 as reported in the '[F]CTT1057 study treatment injection' page of the eCRF will be summarized (with % based on the total number of SAF participants unless otherwise specified ):

- Descriptive statistics of radioactivity dose administered (MBq) •
- Number (%) of participants who were dosed but with problems (i.e. extravasation) in • administration
- Number (%) of participants with dose administered outside the planned range (i.e. < 266٠ MBq or > 407 MBq)
- Time (in minutes) from injection to full-body PET imaging acquisition start time (based on the '[F]CTT1057 PET/CT Imaging - Local reads' page)
- Number (%) of participants with additional pelvic PET imaging acquisition, with time (in • minutes) from injection to additional pelvic PET imaging acquisition start time, if applicable (based on the '[F]CTT1057 PET/CT Imaging - Local reads' page)
- Time (in days) from full-body PET imaging acquisition start time to the date of surgery • (based on the '[F]CTT1057 PET/CT Imaging - Local reads' page and the 'Radical prostatectomy and ePLN dissection - Local histopathology assessment' page)

Participant level listings of doses administered or not, along with reasons if not administered will be produced using the FAS.

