#### 2.8.3 Laboratory data

Laboratory data from all sources (central and local laboratories) will be combined for the analysis. The summaries will include all assessments available for the lab parameter collected prior to (baseline) and during the on-treatment period (14 + 3 day-window) after the study treatment administration.

All laboratory data will be listed by participant and visit/time and if normal ranges are available abnormalities will be flagged. Summary statistics will be provided by visit/time. Shift tables using the low/normal/high/ (low and high) classification will be used to compare baseline to the worst on-treatment value.

Grading of laboratory values will be assigned programmatically as per National Cancer Institute (NCI) CTCAE version 5.0. The calculation of CTCAE grades will be based on the observed laboratory values only, clinical assessments will not be taken into account.

CTCAE Grade 0 will be assigned for all non-missing values not graded as 1 or higher. Grade 5 will not be used.

For laboratory tests where grades are not defined by CTCAE version 5.0, results will be categorized as low/normal/high based on laboratory normal ranges.

The following listings/summaries will be generated separately for hematology and biochemistry tests:

Novartis	Confidential	Page 31 of 43
SAP Amendment 2		Study No. CAAA405A12302

• Listing of all laboratory data with values flagged to show the corresponding CTCAE version 5.0 grades if applicable and the classifications relative to the laboratory normal ranges.

For laboratory tests where grades are defined by CTCAE version 5.0:

- Worst post-baseline CTCAE grade (regardless of the baseline status). Each participant will be counted only once for the worst grade observed post-baseline.
- Shift tables using CTCAE version 5.0 grades to compare baseline to the worst ontreatment value

For laboratory tests where grades are not defined by CTCAE version 5.0:

• Shift tables using the low/normal/high/ (low and high) classification to compare baseline to the worst on-treatment value.

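### Post-operative events in men operated on within 14 days of dosing enter the all-causality TEAE, SAE and worst-laboratory-value tables, and no planned table separates them

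*SAP*

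**What the plan says.** **Timing of surgery.** Protocol section 3 (Additional Follow-up) places surgery "on a date that must not be sooner than 48 hours after the completion of the" scan and "no later than 6 weeks after completion of the" scan. Protocol section 3 and SAP 1.1 give the reason for the 48-hour gap: "in order to limit the potential confounding factors related to the effects of surgery" on the safety assessment. If surgery comes before the Day 15 visit, the visit's assessments are done before the operation and not repeated (protocol Table 8-1 footnote 11 and section 8.4).

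**Safety endpoint and window.** Protocol Table 2-1 names the endpoint as the incidence of AEs, with "Treatment emergent adverse event (TEAE) rate within 14 days of administration". SAP 2.1.1 sets the on-treatment period as "from day of dosing of study medication to 14 days after dosing of study medication", and protocol 12.5.2 uses the same definition. SAP 2.8.1 summarises all AEs that begin or worsen in that period, with no filter on cause. AE monitoring (protocol 10.1.1) and all-causality SAE reporting (protocol 10.1.3) also run to 14 days after the dose, whether or not surgery has taken place.

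**Laboratory data.** SAP 2.8.3 states: "Laboratory data from all sources (central and local laboratories) will be combined for the analysis". It uses a 14 + 3 day window and compares baseline with the worst on-treatment value.

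**What is already planned that helps.** Protocol 12.5.2 and SAP 2.8.1 include separate summaries of AEs and SAEs related to study treatment. SAP 2.4.1 already derives the time from "full-body PET imaging acquisition start time to the date of surgery".

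**The concern.** The plan treats surgery as a confounder of tracer safety and acts on that in two places: the first 48 hours and the scheduled safety visit. It does not act on the window over which events are counted. Nothing in either document ends that window at surgery, flags events that start after it, or splits the tables by it.

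The trial has a single arm, so no comparison group carries the same surgical background. For men operated on within 14 days, post-operative events are added to the named secondary safety rate. Two sets of sites with identical tracer safety could report different TEAE rates only because one set operates sooner.

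**Working it through.** The documents state no expected TEAE rate, so there is no figure of theirs to reproduce. The check has two parts.

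**1. Overlap of the windows (inputs from the documents)**
- Earliest surgery: 48 hours after the scan, about day 2 after dosing.
- Latest surgery: 6 weeks, or 42 days.
- TEAE window: 14 days after dosing.
- Largest post-operative part of the window: 14 - 2 = 12 days, and 12/14 = 86%.
- Share operated on inside the window, if surgery dates were spread evenly over days 2 to 42 (an assumption): (14 - 2)/(42 - 2) = 12/40 = 30%. Of about 195 enrolled, that is 0.30 × 195 = 58.5 men.

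**2. Effect on the TEAE proportion (all three inputs are assumptions)**
- *f*: share operated on within 14 days, 5-50%.
- *c*: chance that such a man has at least one post-operative AE recorded inside the window, 20-90%.
- *b*: proportion with a TEAE unrelated to surgery, 5-20%.

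Taking the two sources of events as independent:

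reported proportion = 1 - (1 - b)(1 - f·c)

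increase = (1 - b)·f·c

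| f | c | b | Reported | Increase (points) |
|---|---|---|---|---|
| 5% | 20% | 20% | 1 - 0.80 × 0.99 = 20.8% | 0.8 |
| 10% | 50% | 5% | 1 - 0.95 × 0.95 = 9.75% | 4.75 |
| 30% | 50% | 20% | 1 - 0.80 × 0.85 = 32.0% | 12.0 |
| 30% | 50% | 5% | 1 - 0.95 × 0.85 = 19.25% | 14.25 |
| 50% | 90% | 5% | 1 - 0.95 × 0.55 = 47.75% | 42.75 |

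The first and last rows are the extremes of the assumed ranges. The increase is never negative, so the direction does not depend on the inputs. In this model, a table that stops at surgery reports *b*, or somewhat less because men operated on early are observed for fewer days.

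**Laboratory route.** Men operated on early have no scheduled safety draw after surgery. Post-operative values can enter only as unscheduled results, for example local ones meeting the criteria in protocol 8.4.1 (such as documenting an AE the central laboratory did not report). Once recorded, they are pooled and can become the worst on-treatment value. The Day 15 by-visit summary takes only results from 14 to 17 days after injection (SAP Table 2-1), so earlier post-operative values stay out of it.

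**The case against.** The strongest reply is that treatment-emergent is a label of timing, not of cause. Causality to the tracer is recorded for every AE (protocol 10.1.1). Related AEs, related SAEs and deaths from related SAEs are tabulated separately (SAP 2.8.1). A surgical complication need not be reported as caused by the tracer. This stands, and it limits the point to the all-causality tables. It does not remove the point, because relatedness is investigator judgement in an open-label study and gives no all-causality rate free of surgery.

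Further objections:
- **SAEs.** Protocol 10.1.2 exempts hospitalisation for routine treatment of the studied indication without deterioration. A reader might infer that each planned operation is counted as an SAE; the documents do not support that. Complications that meet the SAE criteria still count.
- **Laboratory data.** The exposure is confined to unscheduled results in the worst-value and shift tables, to an unknown extent. This stands.
- **Size.** No input to the calculation comes from the documents. Surgery dates need not be evenly spread, since the local scan report goes to the treating physician before surgery (protocol 8.3.1). Some men may not be operated on at all (protocol 4.1). This stands, which is why only a range is given.
- **The fixed window.** It gives every man the same observation period and matches AE and SAE collection. A window ending at surgery can be as short as about 2 days. This is a good reason to keep the 14-day table as the endpoint, but not a reason to omit the split.
- **Consequence.** Safety is secondary and descriptive, and study success rests on the two diagnostic co-primary endpoints. This stands.

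**Conclusion.** The point holds in a limited form. For men operated on within 14 days of dosing, post-operative AEs and SAEs and any recorded unscheduled post-operative laboratory values enter the overall TEAE, SAE and worst-grade or shift tables. The bias is upward and varies with surgery timing. Its size is unknown: about 1 to 43 percentage points under the assumed ranges, which cover surgery timing, post-operative AE recording and the background rate. The overlap of up to 12 of 14 days follows from the documents; the percentage-point range does not.

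Two stronger readings are tempting. One is that the reported rates say nothing about tracer safety. The related-event tables argue against that, and men operated on after day 14 are unaffected. The other is that a particular inflated rate can be predicted against a known true rate. The documents give neither. The co-primary endpoints are not touched. This is an inexpensive improvement to the description of tracer safety.

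**What to change.** In SAP 2.1.1, 2.8.1 and 2.8.3, and in protocol 12.5.2:

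1. Keep the fixed 14-day tables as the named endpoint.
2. Add pre-specified tables of TEAEs, SAEs and worst laboratory grades with onset (or sampling) from dosing to the earlier of surgery or 14 days. Report the days observed.
3. Add a separate table for events from surgery to day 14, including any judged related to the tracer.
4. Use the pre-surgery table when describing tracer safety.
5. State in advance where events dated on the day of surgery fall, and how partial onset dates are placed. SAP Table 5-1 can set a partial start date to the dosing date, which would move a post-operative event into the pre-surgery table.

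The cost is SAP and protocol wording and one extra set of tables. The surgery date is already used in SAP 2.4.1, so no new data are needed. The downside is shorter observation in men operated on early, which the reported days make visible. Surgery timing does not change.

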 For a subset of approximately 10 participants from the same clinical site consenting for the PK sample collection

 Vital signs will be performed at screening, at PET imaging day (pre and post-injection and prior to discharge) and at Safety Follow-up visit

 Peripheral venous blood samples will be collected at screening and PET imaging day pre-injection and at Safety follow-up (Day 15)

 Urine samples will be collected at screening, at PET imaging day and Safety Follow-up and analyzed at the clinical site if dipstick results are abnormal

 For 10 participants from the same clinical site, blood and urine samples will be collected for PK analysis, refer to [Section 8.5.1](#) of the protocol

 Order to be placed after enrollment and based on drug availability local timelines (refer to Pharmacy Manual) in order to perform PET imaging Day 1 no more than 14 days after enrollment.

 Participant will be injected intravenously approximately 370 MBq (range 266–407 MBq) of [F]CTT1057, flushed with 10 mL saline

 [REDACTED] after [F]CTT1057 imaging agent injection, a CT will be obtained from vertex to mid-thighs, followed by static PET emission scan over same area starting from mid-thighs

 Histopathology results must be obtained within up to 2 weeks following RP with ePLND, which must be planned within up to 6 weeks after but not sooner than 48 hours after PET Imaging Day

 For participants undergoing surgery prior to planned safety visit, these safety follow-up assessments will need to be performed before the surgery and not sooner than 48 hours after the PET scan and in that case safety assessments are not to be repeated on Day15

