### **Adverse events**

All information obtained on adverse events will be displayed by participant.

The number (and percentage) of participants with TEAE (events started after the first dose of study medication or events present prior to start of study treatment but increased in severity based on preferred term) will be summarized in the following ways:

- primary system organ class and preferred term.
- primary system organ class, preferred term and maximum severity.
- Standardized MedDRA Query (SMQ) and preferred term.

Separate summaries will be provided for study medication related adverse events, death, serious adverse events.

A participant with multiple adverse events within a primary system organ class is only counted once towards the total of the primary system organ class.

Summary tables for AEs will include only AEs that started or worsened during the on-treatment period, i.e. the **treatment-emergent** AEs.

The incidence of treatment-emergent adverse events (new or worsening from baseline) will be summarized by system organ class and or preferred term, severity (based on CTCAE grades), type of adverse event, relation to study treatment.

Serious adverse events, non-serious adverse events during the on-treatment period will be tabulated.

All deaths (on-treatment and post-treatment) will be summarized.

All AEs, deaths, and serious adverse events (including those from the pre and post-treatment periods) will be listed and those collected during the pre-treatment and post-treatment period will be flagged.

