#### Windows for multiple assessments

In order to summarize weight, vital signs, ECGs, and laboratory tests collected over time (including unscheduled visits), the assessments will be time slotted. The following general rule will be applied in creating the assessment windows: If more than one assessment is done within the same time window, the assessment performed closest to the target date will be used. If 2 assessments within a time window are equidistant from the target date, then the earlier of the 2 assessments will be used. If there are multiple assessments on the same date, then the worst

Novartis	Confidential	Page 16 of 43
SAP Amendment 2		Study No. CAAA405A12302

case will be used. Data from all assessments (scheduled and unscheduled), including multiple assessments, will be listed.

Table 2-1	Time windows	
Time Window	Planned Visit Timing	Time Window Definition
On treatment		
Baseline (pre-treatment)	On or before Study Day 1*	Before Study Day 1, or on Study Day 1 but prior to [  F]CTT1057 injection
Day 1	Study Day 1	Date of [  F]CTT1057 injection
Day 15	Study Day 15	$14 - 17$ days after the date of $[^{18}F]CTT1057$ injection

\*Study Day 1 = the date of  $[^{18}F]$ CTT1057 injection

Electrocardiograms (ECGs) (for the PK subset) and vital signs will be assessed pre-injection, post-injection/ pre-imaging and post-imaging on Study Day 1. Their results will be presented by timepoint.

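### The safety periods in SAP 2.1.1 and the Day 1 window in Table 2-1 overlap before the injection on Day 1, so the pre-injection laboratory sample fits both baseline and on-treatment, in conflict with the dose-tied rules elsewhere

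*SAP*

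**What the plan says.** SAP 2.1.1 (On-treatment assessment/event and observation periods) states that "the overall observation period will be divided into three mutually exclusive segments". Pre-treatment runs "from day of participant's informed consent to the day and time before dosing of study medication". On-treatment runs "from day of dosing of study medication to 14 days after dosing of study medication". Protocol 12.5.2 defines the periods in the same words.

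SAP Table 2-1 slots weight, vital signs, ECGs and laboratory tests into windows. Baseline is "Before Study Day 1, or on Study Day 1 but prior to" the injection. The Day 1 window is simply the date of injection. A sentence under the table says that vital signs and PK-subset ECGs are shown by timepoint; it does not mention laboratory tests.

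On sampling, footnote 4 of protocol Table 8-1 reads "Peripheral venous blood samples will be collected at screening and PET imaging day pre-injection and at Safety follow-up (Day 15". Protocol 8.4.1 also requires the safety laboratory samples to be taken before administration.

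The laboratory shift tables in SAP 2.8.3 "will be used to compare baseline to the worst on-treatment value".

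Other rules count from the dose:
- Protocol 12.5.2 (Adverse events) takes as treatment-emergent "events started after the first dose of study medication", or earlier events that worsened.
- SAP 2.8.1 takes events that started or worsened within 14 days after the dose, plus events reported as tracer-related.
- SAP 2.8.3 places on-treatment laboratory values in a 14 + 3 day window following administration.

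**The concern.** The hours before the injection on Day 1 belong to two periods that are meant to exclude each other. This matters for laboratory data because the only scheduled safety sample that day falls in those hours, and it will normally be the baseline. If it is also on-treatment, the shift tables compare baseline with a set that contains baseline. An abnormality that resolves by follow-up would be shown as persisting, and a man with no post-injection sample would be shown as assessed and unchanged.

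For adverse events, a reaction to blood sampling or cannulation shortly before the injection is pre-treatment by clock time and on-treatment by calendar day. The treatment-emergent rate within 14 days is a secondary safety endpoint, and a single-arm study has no control group against which to set a misattributed event.

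**Working it through.** The plan states no figure that depends on this boundary, so there is nothing to reproduce. The check is to classify one record, taken on Day 1 an hour before the injection, under each written rule.

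| Rule | Boundary | Record included? |
|---|---|---|
| SAP 2.1.1 and protocol 12.5.2, pre-treatment | day and time of dosing | yes |
| SAP 2.1.1 and protocol 12.5.2, on-treatment | calendar day of dosing | yes |
| SAP Table 2-1, Baseline | before injection | yes |
| SAP Table 2-1, Day 1 | whole date of injection | yes |
| Protocol 12.5.2, treatment-emergent event | after the dose | no |
| SAP 2.8.1, treatment-emergent event | within 14 days after the dose | no, unless it later worsened or was reported as tracer-related |
| SAP 2.8.3, laboratory on-treatment window | after administration | no |
| SAP 2.8.3, worst post-baseline CTCAE grade | after baseline | no, if it is the baseline value |

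The record is double-classified by the general definitions and excluded by the specific ones.

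**Consequence of a literal reading of 2.1.1 and Table 2-1.** The scheduled on-treatment laboratory values are then two: the pre-injection Day 1 sample and the follow-up sample. The first is the baseline, so the worst of the two cannot be better than baseline, whatever the follow-up shows. The scheduled Day 1 laboratory row contains only pre-injection values and repeats baseline.

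**Illustration of size.** The documents give neither abnormality rates nor within-patient correlations, so both are assumed here. Let a parameter be abnormal with probability p at each of the two visits, with a bivariate normal latent variable of correlation ρ and no tracer effect.

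P(abnormal at either visit) = 2p − P(abnormal at both).

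- p = 0.10, ρ = 0.5: P(both) = 0.0324, so 0.20 − 0.0324 = 0.168, or 1.68 times the true 0.10.
- p = 0.10, ρ = 0.9: P(both) = 0.0689, so 0.20 − 0.0689 = 0.131, or 1.31 times.
- p = 0.05, ρ from 0.9 to 0.5: 6.8% to 8.8%.
- p = 0.20, ρ from 0.9 to 0.5: 25.0% to 31.3%.

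The share of baseline-abnormal men who are in fact normal at follow-up is 1 − P(both)/p. At p = 0.10 this is 1 − 0.0689/0.10 = 31% to 1 − 0.0324/0.10 = 68%. The literal shift table would show none of them.

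On a continuous scale with no true change, including baseline in the set raises the mean worst value, relative to follow-up alone, by SD × √(2(1 − ρ))/√(2π). That is 0.40 SD at ρ = 0.5, 0.25 SD at 0.8 and 0.18 SD at 0.9.

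**After the fix.** With the boundary at the time of injection, the record is pre-treatment and Baseline only, the periods are mutually exclusive, and one scheduled on-treatment laboratory value remains, the follow-up sample. Records after the injection on Day 1 do not move.

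**The case against.** The best defence is that the specific rules already give the right answer. The period list in SAP 2.1.1 is introduced as being for adverse event reporting, and SAP 2.8.3, where the shift tables are specified, has its own window starting after administration. The worst post-baseline CTCAE grade table cannot be affected, since a baseline value is not post-baseline. For adverse events, the clock-time end of pre-treatment, the stated exclusivity and the dose-tied definitions all point to pre-treatment.

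Much of this stands. A reader might infer that Day 1 events before the injection definitely count as treatment-emergent; the documents do not support that, because protocol 12.5.2 and SAP 2.8.1 exclude them. Nor is every Day 1 blood draw pre-injection: protocol Table 8-6 schedules PK samples afterwards, and the point concerns safety laboratory samples only.

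It does not dispose of the point. SAP 2.1.1 goes on to restrict safety summaries generally, not just adverse event tables, to the on-treatment period. Table 2-1 expressly covers laboratory tests and has no time split on Day 1. SAP 2.8.1 refers back to 2.1.1, which classifies events by start date. Nothing says which rule prevails. Protocol 10.1.1 asks for event start and end dates and mentions no clock time, so a date-only implementation is plausible. By the same token, if onset times are not collected, correcting the boundary will not change the adverse event counts.

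**Conclusion.** The inconsistency is real and can be read directly from the text: two periods declared exclusive overlap, two analysis windows overlap in the same place, and both disagree with the dose-tied rules. Taken literally, SAP 2.1.1 and Table 2-1 make improvement from baseline impossible to show in the laboratory shift tables and turn the Day 1 laboratory summary into a copy of baseline.

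The documents do not establish that the tables will be produced that way, since SAP 2.8.3 supports the correct reading. The 1.31 to 1.68-fold range is therefore not an estimate for this trial. It applies only to the literal reading and only under the assumed 10% prevalence and correlation of 0.5 to 0.9. Pre-injection Day 1 adverse events are inconsistently classified, and the number affected cannot be derived.

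Priority is low. Only descriptive safety tables are involved. The co-primary endpoints, the hypotheses and the sample size are untouched, and all laboratory values are listed by participant and visit in any case.

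**What to change.** - In SAP 2.1.1, start the on-treatment period at the date and time of injection. Keep Day 1 adverse events without an onset time as on-treatment, so that no possible tracer event is lost.
- Align the same wording in protocol 12.5.2, or record the difference in SAP Section 4.
- In Table 2-1, define the Day 1 window as the date of injection, after the injection. Pre-injection laboratory samples then go to Baseline only, and no scheduled Day 1 laboratory row is produced. Keep the by-timepoint display of vital signs and PK-subset ECGs.
- In SAP 2.8.3, state that only post-injection values enter the worst on-treatment laboratory result.

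The cost is a few lines of wording and one date-time condition in programming. The remaining limitation is that events without an onset time still rely on the conservative default.
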